INVASIVE

INFLUENCE OF PRENATAL COUNSELING IN INVASIVE TESTING

PROTOCOL FOR A RANDOMIZED CONTROLLED TRIAL

[name]

[name]

[name]

[name]

Hospital Clinic of Barcelona / University of Barcelona

Study Number: IRN2019/03/0001

Human Subjects Review Approval: HCB/2019/0788

September 15th, 2019

Study design:

This is a randomized open-label controlled trial evaluating the impact of an extra 15-minute prenatal counseling before the first trimester combined screening test for Down's syndrome, on the women's attitudes and preferences towards having an invasive testing as the first line option for screening of chromosomal abnormalities.

Data will be collected by the study-site manager and stored in an electronic data-capture database. The coordinator of the study and the statistician will witness the accuracy of the data at the beginning, middle, and end of the study (on-site audit). Data will be captured in a paper form basis and then captured into the electronic database.

Participants

Inclusion criteria: any pregnant woman of at least 18 years old, attending the first trimester combined screening test for chromosomal abnormalities (between 11+0 and 13+6 weeks' gestation). The exclusion criteria: women not willing to participate in the study, women without an answer in the question regarding which prenatal test would they choose (main outcome), or women with no sufficient knowledge of Spanish or Catalan to be able to read and understand the questionnaire.

Intervention and procedures

For the experimental group, the intervention will consist of an extra 15-minute prenatal counseling before their first trimester scan. This intervention will require an explanation of all screening techniques for chromosomal abnormalities, including the first trimester combined test, cfDNA testing, invasive testing, and no screening at all. The intervention will be given by a single maternal-fetal medicine specialist who will explain all pros and cons of all given methods, giving also time to solve any question the woman may have. After the intervention (counseling), all participants will be asked to fill a questionnaire of twenty-one question regarding their knowledge, attitude and preferences about prenatal testing.

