The first fourteen questions consist of demographic characteristics and obstetrics history, such as age, ethnicity, study level, marital status, religion, salary, employment, parity, previous miscarriages, previous terminations of pregnancy, previous congenital defects, pregnancy search time in months, type of conception, and who had provided any type of previous information about prenatal screening/testing. Women will be asked to select only one option for each question. All questions will have the possibility to answer as “Prefer not to answer”. The second part of the questionnaire will assess the preferences and attitudes towards prenatal testing; women will be asked to choose only one option for each question. The following questions will be included in the second part of the questionnaire: What influences you the most about prenatal testing? Who influenced you the most about prenatal testing? Would you like to choose your prenatal test? Which prenatal test would you choose? What is your opinion about termination? All questions include an “I don’t know answer”. The two final questions will ask the following, “What information regarding the results of prenatal testing is more important for you?” and “What is most important for you about prenatal testing?”. Women will be asked to score the first question from 1 to 5, meaning 1 the least important and 5 the most important, and from 1 to 6 in the same manner for the second question. These two questions will be assessed as means, where the question with the highest mean represents what is most important for the patient.

Outcomes

The primary outcome of the study is the desire to choose an invasive diagnostic testing as the first option of screening for chromosomal abnormalities. This will be measured in the questionnaire by asking the question: which prenatal test would you choose if given the opportunity? Women will be asked to choose only one answer between first trimester combined test, cell-free DNA, invasive testing.

Statistical analysis

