Analysis will be conducted by intention-to-treat. Missing data for the main outcome will be handled by complete-data analysis because women without an answer on the main outcome will be excluded. All analyses will be divided by groups (control vs experimental group). Continuous data will be assessed for normality using the Kolmogorov-Smirnoff test. Normally distributed variables will be compared using t-test and expressed as mean and standard deviation (SD), while not normally distributed variables will be analyzed using the Mann-Whitney-U test and expressed as medians and interquartile range (IQR). Quantitative variables will be

compared using X^2 test and expressed as numbers (n) and proportions (%). For the main outcome, preferences for prenatal testing among groups will be analyzed using absolute risk increase defined as the incidence of the outcome in the experimental group minus the incidence in the control group. The absolute risk increase will be depicted in a forest plot. A multivariate logistic regression will be performed to determine the Odds for choosing an invasive testing adjusting by demographic characteristics and previous counseling. Data will be analyzed using STATA v.15.3 for Mac (Texas College Station) and GraphPad Prism version 8.1.2 for Mac, GraphPad Software, San Diego, California USA, www.graphpad.com.

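### The counselling presents having no screening as an option, but the primary question as described has no answer that records it

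*Combined protocol and SAP*

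**What the plan says.** Under Intervention and procedures, the extra counselling explains every approach to chromosomal abnormalities, "including the first trimester combined test, cfDNA testing, invasive testing, and no screening at all". That is four courses. Control women go straight to the questionnaire.

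Under Outcomes, the endpoint is defined as follows: "The primary outcome of the study is the desire to choose an invasive diagnostic testing as the first option of screening for chromosomal abnormalities". For the item that measures it, "Women will be asked to choose only one answer between first trimester combined test, cell-free DNA, invasive testing". The Questionnaire section adds, after a list of items that includes this one, "All questions include an “I don’t know answer".

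Two places deal with a missing answer. Participants lists among the exclusions "women without an answer in the question regarding which prenatal test would they choose (main outcome". Statistical analysis, after stating intention-to-treat, says "Missing data for the main outcome will be handled by complete-data analysis because women without an answer on the main outcome will be excluded". For the main outcome, the same section says that "preferences for prenatal testing among groups will be analyzed using absolute risk increase", shown in a forest plot.

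**The concern.** The intervention puts four courses in front of a woman, and the instrument that measures its effect lets her name three. A counselled woman who decides that she wants no test has a definite preference and no answer that states it. She can tick a test she does not want, say that she does not know, or leave the item blank.

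Only the experimental arm hears from the trial that declining is an option, so the gap need not fall equally on the two arms. Counselling could move some women toward invasive testing and others toward no testing, and the plan as described can show only the first. The shares choosing each test, which are compared between arms, could be distorted. The estimate for invasive testing could also be affected, depending on how these women respond and how their responses are handled.

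**Working it through.** **1. Is declining recorded anywhere else?** The described items add up to the whole questionnaire: 14 on demographics and obstetric history, 5 named preference questions and 2 scoring questions, 14 + 5 + 2 = 21. One preference question asks whether the woman would like to choose her test; that concerns wanting a choice, not refusing one. A refusal-to-answer option is mentioned in the description of the first fourteen items; even if it reached the primary item, it would not state a wish for no screening. No outcome on actual uptake is planned, and Follow-up after the intervention sends both arms to routine combined screening. As described, nothing captures the preference.

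**2. The plan's sample size.** Inputs from Sample size: 10% in controls, a 25% difference read as absolute (35%), likelihood-ratio test, two-sided, 80% power. With H(p) = −[p ln p + (1−p) ln(1−p)] and mean proportion 0.225, the noncentrality is 2n[2H(0.225) − H(0.10) − H(0.35)]. At n = 42 the power is 0.8015 with alpha 0.05 and 0.8017 with the stated 0.0501; at n = 41 it is 0.792. So 42 per arm reproduces. A relative reading (10% against 12.5%) would need about 2,506 per arm by the pooled normal formula, which confirms the absolute reading.

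**3. What each response does.** Let q be the fraction of counselled women who want no screening.

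| Response | Invasive or not | Breakdown by test |
|---|---|---|
| Combined test or cell-free DNA | Correct: not invasive | Those categories overstated by q in total |
| Invasive testing | Experimental rate too high | Invasive share overstated |
| 'I don't know', kept as not invasive | Correct | A decided woman shown as undecided |
| 'I don't know', treated as no answer | Excluded, as for a blank | Other shares inflated |
| Blank | Excluded after randomization | Other shares inflated |

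The plan does not say how 'I don't know' is counted.

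**4. Size of the exclusion route.** The documents give no q, so 5% and 10% are assumptions. Assume also that no control opts out and that every opt-out leaves a blank. Expected invasive choosers in the experimental arm: 0.35 × 42 = 14.7.

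- q = 5%: 14.7 / (42 × 0.95) = 14.7 / 39.9 = 36.8%. Difference 36.8 − 10 = 26.8 points, a bias of +1.8.
- q = 10%: 14.7 / (42 × 0.90) = 14.7 / 37.8 = 38.9%. Difference 28.9 points, a bias of +3.9.
- No true effect, 10% in both arms: 10% / 0.95 = 10.5% and 10% / 0.90 = 11.1%, biases of +0.5 and +1.1 points.

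Weaker assumptions shrink this. If 5% opt out in both arms and all leave blanks, the difference is 25 / 0.95 = 26.3 points (+1.3). If 5% of counselled women opt out and one third of them leave a blank, the experimental rate is 35% / (1 − 0.0167) = 35.6% (+0.6).

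**5. Size of the forced-tick route.** If opt-outs spread evenly over the three tests, the experimental invasive rate rises by q/3: 1.7 points at 5% and 3.3 points at 10%. If all tick a non-invasive test, the bias is zero.

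**The case against.** A reader might infer that every woman who wants no screening is misclassified or lost from the primary result, and that the plan therefore overstates the effect of counselling. The documents do not support this. The endpoint is binary, and a woman who ticks the combined test or cell-free DNA is still correctly counted as not choosing invasive testing.

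The other objections are these.

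- **The inflation belongs to another rule.** The figures in step 4 come from excluding unanswered items after randomization, which also sits badly with the stated intention-to-treat analysis. If blanks were kept as not invasive, the same three boxes would give no inflation. This stands. What belongs to the answer list itself is the unrecorded preference, the distorted breakdown and any forced tick.
- **Opt-outs may be few.** Participants are women already "attending the first trimester combined screening test for chromosomal abnormalities". This stands as a limit on size, though attendance before counselling does not show what a woman prefers after it.
- **Controls are not uninformed.** The questionnaire asks who gave earlier information, and the regression adjusts for previous counselling. Zero opt-outs among controls is therefore an extreme assumption. This stands.
- **The form is not in the document.** The list under Outcomes omits 'I don't know', which the Questionnaire section says is there, so the list is not complete and the form may hold another box. This stands: the point concerns the plan as described.
- **Declining is outside the stated aim.** Study design asks about invasive testing as a first-line choice. This stands in part. No objective on declining is stated, but the intervention itself presents that course, and the analysis compares preferences among tests between arms.

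**Conclusion.** The point holds, with moderate confidence, for the plan as described. A preference for no screening cannot be recorded as such, the comparison of preferences by test can be distorted, and the trial cannot say whether counselling led women to decline.

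For invasive versus not, bias is conditional on the three routes in step 3: a forced invasive tick, a blank that is excluded, or an 'I don't know' treated as no answer. With an assumed 5% to 10% of counselled women opting out, the exclusion route adds at most 1.8 to 3.9 points to a true difference of 25, and 0.5 to 1.1 points when there is no effect. The latter is far too little to produce a result like the planned 25 points. These are upper illustrations of that route and not estimates, because the documents give no opt-out rate. The gap limits what the trial can report and may bias its estimate; it does not invalidate the trial.

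**What to change.** Add 'No screening or testing' as a substantive answer to the primary question in both arms, so that the answers match the four courses in the counselling. State under Outcomes that it counts as answered and not invasive, so the woman stays in the denominator. Report its proportion by arm beside the other choices, including in the forest plot. In the same edit, state how 'I don't know' is counted, and reconcile the answer list under Outcomes with the Questionnaire section. If the form already has such a box, correct the list under Outcomes and state how the box is counted.

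The cost is one response box, a sentence or two of text and one more row in the results, with answers spread over one more category. The binary outcome definition and the 42 per arm do not change. The box has to be on the form before women complete it, because the preference cannot be recovered from the collected answers.

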For the control group, women will not be given an extra 15-minute counseling (no intervention), but will be directly asked to fill the questionnaire about their knowledge, attitude and preferences about prenatal testing.

Sample size

Sample size calculation has been made using an independent two-sample proportions likelihood-ratio test. We expect a 10% of women willing to have an invasive procedure as a first line test for aneuploidies in the control group, and a 25% difference to those in the experimental group that are given an extra 15-minute prenatal counseling, this yields a sample of 42 women per arm with a total of 84 subjects using a Type I error of 0.0501 and a power of 80% by a two-sided test.

Randomization and intervention

Participants will be randomized using an interactive Web-response system assigning patients in a 1:1 ratio to receive the extra counseling before first trimester assessment (intervention group) or nothing (control group). The allocation will be performed by the study manager. The maternal-fetal medicine specialist will be in charge of the participant's enrolment and will also perform the intervention to the corresponding randomized group. This is an open-label study which means that the specialist and women will be aware of the allocation and intervention every time.

Follow-up after the intervention

After both groups (the experimental and control) have filled the questionnaire, the routine prenatal care will be given according to our hospital's guidelines, which consists of a first trimester ultrasound scan, and the subsequent risk calculation for trisomy 21 and 18 with the use of the first trimester combined test. In case of risk greater than 1/250, an invasive diagnostic test will be offered. For risks between 1/250 and 1/1,000 a complementary first trimester genetic sonogram using secondary markers (nasal bone, tricuspid regurgitation, and ductus venosus) will be offered to re-calculate the risk for Down's syndrome. For women with Down's risk greater than 1/1000, no further evaluations will be offered.

Questionnaire

The questionnaire consists of twenty-one questions assessing the knowledge, preferences and attitude towards prenatal testing in the first trimester of pregnancy. The questionnaire will be divided in two parts.

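### The adjusted logistic regression has an open covariate set and about 19 expected events; if the planned effect is real and all the demographic items enter, its odds ratio tends to be too large and imprecise

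*Combined protocol and SAP*

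**What the plan says.** The Statistical analysis section analyses the main outcome by the absolute risk increase, experimental minus control. It then adds one sentence on a model: "A multivariate logistic regression will be performed to determine the Odds for choosing an invasive testing adjusting by demographic characteristics and previous counseling". It gives no covariate list, coding, selection rule or method for sparse data. The only missing-data rule concerns the main outcome.

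The candidate covariates are in the Questionnaire section: "The first fourteen questions consist of demographic characteristics and obstetrics history, such as age, ethnicity, study level, marital status, religion, salary, employment, parity", followed by further obstetric items. No item is called previous counselling. The nearest asks "who had provided any type of previous information about prenatal screening/testing". On format, the section says "Women will be asked to select only one option for each question", but it does not give the options. Women may also decline any of these items: the sentence starting "All questions will have the possibility to answer as" provides for it.

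The Sample size section supplies the rates: "We expect a 10% of women willing to have an invasive procedure as a first line test for aneuploidies in the control group", "a 25% difference to those in the experimental group that are given an extra 15-minute prenatal counseling", and "this yields a sample of 42 women per arm with a total of 84 subjects".

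**The concern.** Ordinary maximum-likelihood logistic regression pushes a non-zero log odds ratio away from zero when events are few relative to the number of coefficients. This trial expects few events, and the wording invites a long covariate list. An adjusted odds ratio for the primary outcome could therefore be reported well above the true one, with a wide interval. The size of the distortion would depend on choices that the plan leaves open. Nor does the plan say what happens to a woman who declines a covariate item. By default the software would drop her, and the few events would become fewer.

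A second difficulty is timing. Under Intervention and procedures, the experimental arm completes the questionnaire after the counselling session. The item on previous information could therefore pick up the session itself, and adjusting for it could remove part of the effect.

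**Working it through.** **Inputs.** From Sample size: control rate 10%, difference 25%, 42 per arm, two-sided type I error 0.0501, power 80%, likelihood-ratio test. From Questionnaire: seven demographic items in the narrow sense (age, ethnicity, study level, marital status, religion, salary, employment) and one item on previous information.

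**The plan's own figure.** With h(p) = p ln p + (1 − p) ln(1 − p), the likelihood-ratio formula is n = (z₁ + z₂)² / {2[h(p₁) + h(p₂) − 2h(p̄)]}.
- With 10% and 35%, n = 41.8, so 42 per arm. This agrees with the plan; power at 42 is 80.2%.
- If 25% were the experimental rate, n would be 98. The difference must therefore mean 25 percentage points.

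**Events and true odds ratio.**
- Events: 42 × 0.10 + 42 × 0.35 = 4.2 + 14.7 = 18.9.
- Odds ratio: (0.35/0.65) / (0.10/0.90) = 4.85.

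**Coefficients.**
- One per item: 1 (arm) + 7 + 1 = 9, so 18.9/9 = 2.1 events each. This is the most favourable coding.
- Three levels per categorical item (assumed): 1 (arm) + 1 (age) + 6 × 2 + 2 = 16, so 18.9/16 = 1.2 events each.

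**Simulation under the planned effect.** Settings were 42 per arm, covariates unrelated to the outcome, age continuous and other items binary or three-level, fitted by ordinary maximum likelihood. Each setting had 2,000 to 10,000 trials. Ranges cover repeated simulations, some with different assumed prevalences.

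| Covariates besides arm | Median OR (truth 4.85) | SD of log OR | Share above truth | At least double (≥ 9.7) | 95% coverage | Wald rejection |
|---|---|---|---|---|---|---|
| 0 | 5.0–5.2 | 0.64–0.66 | 53–54% | 18–19% | 97% | 79% |
| 2 | 5.2–5.4 | 0.67–0.69 | 55% | 20–21% | 97% | 79% |
| 8 (one coefficient per item) | 6.2–6.3 | 0.81–0.82 | 64% | 29–31% | 95–96% | 79% |
| 15 (three-level items) | 8.3–9.0 | 1.16–1.20 | 73% | 46% | 92% | 77% |

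The 8.3 comes from a run that dropped the 34% of fits with separation or non-convergence.

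**No effect, at the plan's control rate.** With 10% in both arms, events are 84 × 0.10 = 8.4. With 8 covariates the median odds ratio is 0.99 to 1.01 and false positives are about 3%. Some coefficient, usually a covariate's, diverges in 37% to 48% of fits, depending on the assumed prevalences and on the divergence rule.

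**Is it only non-collapsibility?** Suppose age and previous information are prognostic, with an assumed odds ratio of 1.5 or 2.0 each, while the arms still average 10% and 35%. The true conditional odds ratio then rises to 5.10 or 5.61, and that rise is not bias. The medians with 8 covariates are 6.68 and 7.94. Since 6.68/5.10 = 1.31 and 7.94/5.61 = 1.42, they remain about 31% and 42% too high.

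**Firth penalised likelihood.** The median odds ratio is about 4.6 to 4.7 with 2, 8 or 15 covariates. Wald rejection under the planned effect is about 77%, 73% and 66%.

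**The case against.** The best defence is that little depends on this model. The main-outcome analysis is unadjusted and unaffected. With one coefficient per item, coverage and rejection are close to those of the unadjusted fit. On the log scale the shift from 4.85 to 6.3 is 0.26, about a third of the estimate's own SD of 0.81. The unadjusted odds ratio already has an 18% chance of being at least double the truth, so much of the 30% reflects a trial of 84 women and not the model. The authors might also enter only two to four items, for which the median is about 5.2 to 5.6. All of this stands, and it limits the weight of the point.

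It does not remove the point. The plan's wording covers demographic characteristics without naming a subset, so fitting it as written leads to the longer list. Depending on the items chosen and their coding, the expected odds ratio runs from about 5.3 to about 9. In an open-label trial it is better to close that choice beforehand.

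A reader might infer that the model risks a false claim of effect. The plan's figures do not support this: at 10% in both arms the odds ratio is centred on 1 and false positives are about 3%. If 22.5% is assumed in both arms, which keeps 18.9 events, false positives are 5.8% with 8 covariates and 7.0% with 15. But 22.5% is not the plan's control rate.

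**Conclusion.** The point holds as a minor to moderate weakness in a secondary estimate. If the planned effect is real and all the demographic items plus previous information enter, the adjusted odds ratio has a median about 30% above the truth (6.3/4.85 = 1.30) under the most favourable coding. With three-level items it is nearly double.

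The direction is firm under a true effect. The size rests on assumptions: how many items enter, their coding and prevalences (the response options are not given), and covariates unrelated to the outcome.

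Two further inferences go too far. The first is that this trial's adjusted odds ratio will certainly be exaggerated: about 64% of fits exceed the truth with 8 covariates, so this is a tendency over repeated trials. The second is that the trial's main conclusion is compromised: the absolute risk increase does not use this model.

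**What to change.** Replace the open adjustment set with arm plus one or two named pre-intervention characteristics with stated coding. Possible wording:

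> As an analysis secondary to the absolute risk increase, choice of invasive testing will be modelled by logistic regression on arm and age (continuous, in years). No other covariate will be added or selected from the data. A woman who declines a covariate item stays in the model, with the value replaced by the overall mean calculated without regard to arm. All other characteristics will be tabulated by arm.

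Age is an example. Previous information may be the second covariate only if it is recorded before the counselling session or is clearly worded to exclude it. Mean replacement is one acceptable rule; a separate response category is another. With two covariates and an assumed 5% declining each, mean replacement gives a median odds ratio of 5.3 with 97% coverage.

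If all the listed items are kept, fit the model by Firth penalised likelihood. With the short list Firth is optional.

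The cost is a few sentences in the analysis section and fewer characteristics adjusted for, although randomisation balances these in expectation. Firth shrinks the odds ratio slightly, to about 4.6 against 4.85. It also lowers Wald rejection under the planned effect to about 77% with 2 covariates, 73% with 8 and 66% with 15, against 79%, 79% and 77% for the ordinary fit. The short list is therefore preferable. Sample size and main analysis do not change.
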